- 1. Determine the relationship between chronic training-related effects of moderate intensity exercise on hippocampal-cortical functional connectivity (FC) and changes in learning from exercise.** Although we have shown that long-term moderate intensity exercise training improves hippocampal-cortical FC, it is unclear how these changes from exercise counteract cognitive aging. Our *hypothesis* is that training-related changes in hippocampal-cortical FC with the Default Network (DN) will improve learning in an array of tasks that require the hippocampus for acquisition of new relational memories, but not in tasks that do not require the hippocampus to learn such as motor or response learning. We test this with a 6-month RCT that compares the effects of moderate vs very light intensity exercise of the same modality (stationary cycling) on learning.
- 2. Determine the relationship between rapid transient effects of a single session of moderate intensity exercise on hippocampal-cortical FC and training-related changes in hippocampal FC and learning from exercise.** Animal studies have shown that exercise rapidly affects hippocampal plasticity following a single exercise session, that effects last up to 1 hour, and occur in the same pathways that benefit from long-term training. These effects

[figure not shown]
may reveal insight about the mechanisms of change from training. Our preliminary data support the *hypothesis* that we can see such rapid effects in humans with fMRI. We test this by assessing acute increases in functional hippocampal-cortical *FC* that are specific to moderate intensity exercise, and determining if this response predicts improvements in hippocampal *FC* and learning from 6 months of exercise training.

3. Determine how moderate intensity exercise changes hippocampal-cortical *FC* and learning. Our data indicate that cardiorespiratory fitness (CRF) is a critical factor in cross-sectional differences of hippocampal-cortical *FC* and learning. CRF reflects complex improvements in vascular, cardiac, and metabolic health from moderate intensity exercise. Given the observed rapid effects, our working *hypothesis* is that the physiological processes leading to improved CRF from moderate intensity exercise are critical to the benefits on hippocampal *FC* and learning. We test this by assessing whether individual differences in training-related changes hippocampal-cortical *FC* and learning are predicted by training-related changes in CRF.

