Computers will be used to store and analyze clinical data and we will address elements of computer security to ensure that the data remain confidential.

17. Overall Data Analysis Approach

The primary analysis concerns the difference in functional connectivity among the chronic treatment groups of moderate intensity (M) and light intensity (L) at the single terminus (last visit) of the 6-month RCT. Multiple regression will be used to regress functional connectivity (FC) on dummy coded group membership, and the stratification variables of age and sex.

Suppose that FC for the i^{th} participant at the end of the study is denoted as y_i ($i = 1, \dots, N$) and group is coded as $grp_i = 1$ if M and $grp_i = 0$ if L. Then the multiple regression model for the primary analysis is

$$y_i = \beta_0 + \beta_1 grp_i + \beta_2 sex_i + \beta_3 age_i + e_i.$$

Under the typical assumption that e_i is normally distributed, the coefficients can be estimated using ordinary least squares. The null hypothesis of interest is that there is no group difference, $H_0: \beta_1 = 0$, which can be evaluated with a t -test. In order to account for missing data, multiple imputation will be used, and the null hypothesis of interest will be evaluated based on pooled estimates using Rubin's rules (23). In order to ensure maximal statistical power for the primary aim, the first analysis will have a single outcome, which is the average FC between the posterior hippocampus, posterior cingulate cortex, and the ventral medial prefrontal cortex. Additional exploratory analysis will be performed on individual connections with adjustment for multiple testing (i.e., adjustment for false discovery rate within a region of interest).

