Dealing with missing data: The primary analysis will be conducted according to the ITT principle, in which participants are analyzed in their assigned group at randomization. Multiple imputation will be used for pooled estimation, which provides unbiased estimates under the ignorable mechanism. It is not possible to determine if a missing data mechanism is ignorable or non-ignorable. In order to address the possibility of a non-ignorable mechanism, a sensitivity analysis using pattern mixture modeling with multiple imputation will be conducted under the framework discussed by Little and colleagues (25).

Assessing effects of adherence and training context: ITT analysis is recognized as the best approach for making sound inferences regarding the treatment effect (26). However, ITT focuses on the effect of treatment assignment rather than on the effect of the treatment for participants who experienced the treatment as defined in the protocol. For example, ITT analysis does not adjust for potential non-adherence (variations in session attendance) or treatment cross-over

(exposure to the treatment intended for another group). In exercise trials both of these issues are theoretically important to examine because (a) mechanistically exercise effects are expected to be strongest in a dose-response manner relative to the prescribed exercise program, and (b) there is significant variability in the extent to which participants achieve the prescribed exercise intensity during their training. For example, the latter issue can occur if participants in the M group have difficulty consistently getting their heart rate up to higher intensities due to physical or motivational constraints; or, in contrast, if participants in the L group enrolled in the study with expectations to work harder and in turn get their heart rate up above the prescribed lighter intensity zone when they are exercising at their home sessions.

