Therefore, in a series of un-blinded exploratory per-protocol analyses (27), we will test the extent to which adherence and training context affects training-induced change in primary outcomes of hippocampal-cortical FC and learning. Based on the issues outlined above, analyses will initially be based on pre-planned definitions of context and adherence. First, we will test the extent to which training heart rate (HR) differed in the lab compared to home sessions as a function of intervention group. Based on preliminary descriptive data, we predict that HR will be higher during home sessions for both groups, but there will be no average group differences in this context effect. Second, we will test all training group effects described above with an additional continuous interaction term for %sessions completed. We predict that greater sessions attended will have a weak to moderate effect on the benefit of M compared to L intensity training. Third, we will test the same group interactions with a continuous interaction term for %sessions in the prescribed HR zone. We predict this will have a moderate to strong effect on primary outcomes, as adhering to the intensity prescription is predicted to have a stronger effect than attendance alone. A final analysis will further unpack the direction of intensity adherence, with negative values indicating the percent of sessions below the prescribed HR zone and positive values indicating the percent of sessions above the prescribed HR zone. This final intensity adherence analysis will test both *whether* and *how* gains in benefits were associated with variations in adherence to prescribed HR intensity.

18. Safety

There are no known risks to participating in the questionnaire assessments or cognitive tests. There may be risks involved in exercising on a motorized bicycle: participants may become fatigued or uncomfortable while exercising. Additionally, there may be a small risk of loss of confidentiality associated with study participation. Listed below are potential risks associated with assessments to be completed throughout the trial:

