Therefore, in a series of un-blinded exploratory per-protocol analyses (4), we will test the extent to which adherence and training context affects training-induced change in primary outcomes of hippocampal-cortical functional connectivity and learning. Based on the issues outlined above, analyses will initially be based on pre-planned definitions of context and adherence. First, we will test the extent to which training HR differed in the lab compared to home sessions as a function of intervention group. Based on preliminary descriptive data, we predict that HR will be higher at home sessions for both groups, but there will be no average group differences in this context effect. Second, we will test all group interactions described above with an additional continuous interaction term for %sessions completed. We predict that greater sessions attended will have a weak to moderate effect on benefit of M compared to L intensity training. Third, we will test the same group interactions with a continuous interaction term for %sessions in the prescribed HR zone. We predict this will have a moderate to strong effect on primary outcomes, as adhering to the intensity prescription is predicted to have a stronger effect than attendance alone. A final analysis will further unpack the direction of intensity adherence, with negative values indicating the percent of sessions below the prescribed HR zone and positive values indicating the percent of sessions above the prescribed HR zone. This final intensity adherence analysis will test both *whether* and *how* gains in benefits were associated with variations in adherence to prescribed HR intensity.

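### The exploratory HR-zone adherence models omit baseline fitness, so a fitness-adherence link that differs by arm could show up as a spurious arm-by-adherence interaction

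*Protocol*

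**What the plan says.** Section 17 of the Protocol, under adherence and training context, sets out regressions that it labels exploratory, un-blinded and per-protocol. Their aim is to test how far "adherence and training context affects training-induced change in primary outcomes of hippocampal-cortical FC and learning". Attendance enters first, "with an additional continuous interaction term for %sessions completed". Heart-rate adherence follows: "we will test the same group interactions with a continuous interaction term for %sessions in the prescribed HR zone". Section 17 of the SAP gives the same sequence. Both predict a moderate to strong result for the heart-rate term, and the SAP's reason is "as adhering to the intensity prescription is predicted to have a stronger effect than attendance alone".

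The models being extended are those described earlier in Section 17. The primary model regresses end-of-study FC on group "and the stratification variables of age and sex". It has no baseline fitness term and no baseline FC term. The Aim 2 model has only group, the acute difference and their interaction. Neither document names a further covariate for the adherence models.

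Three other places bear on the point:

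- Protocol Section 5, Aim 3, says that CRF "is a critical factor in cross-sectional differences of hippocampal-cortical" FC and of learning.
- Protocol Section 17 says that M participants may have "difficulty consistently getting their heart rate up to higher intensities due to physical or motivational constraints". For L participants it names a different reason: they may have enrolled expecting to work harder and so overshoot at home.
- Protocol Section 15 has the M target rise in steps to 70-80% of heart rate reserve from week 13. The L arm has only an upper limit, at or below 40%.

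**The concern.** Zone adherence is not randomised. A baseline variable that drives both zone adherence and FC confounds their association, and CRF is a natural candidate. The protocol ties it to FC and learning directly. It ties it to missed zones by plausible inference, since physical constraints on reaching a high heart rate could include low fitness.

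Such confounding would bias the adherence slope within an arm. It reaches the interaction, which is the term to be tested, only if the fitness-adherence link differs between arms. The zone definitions make that possible: fitness could help an M participant reach the zone and have no bearing, or an opposite one, on whether an L participant stays under the ceiling.

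What is at stake is interpretation. The plan predicts a clear result for zone adherence and words the question as what adherence *affects*. A spurious interaction in the predicted direction would look like the expected dose-response.

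**Working it through.** **Figures in the plan.** The plan gives no operating characteristic for the adherence models, so there is none to reproduce. The one input it supplies is sample size: 120 randomised 1:1, less the allowance of 18, leaves 120 - 18 = 102, or 51 per arm.

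**Assumptions.** The documents give no correlations and no alpha. I assume:

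- r = correlation of baseline CRF with end-of-study FC, 0.2 to 0.4;
- a_M and a_L = correlation of baseline CRF with zone adherence in each arm;
- rho = correlation of CRF with age, -0.4;
- two-sided alpha 0.05, and no true effect of arm or adherence.

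**Size of the spurious interaction.** Take standardised FC = r x CRF + noise and zone adherence = a x CRF + noise. After adjustment for age, the slope of FC on adherence within an arm is approximately

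b(a) = r x a x (1 - rho²) / (1 - a² x rho²),

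and the spurious interaction is b(a_M) - b(a_L). With rho² = 0.16:

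- r = 0.3, a_M = 0.5, a_L = 0: 0.3 x 0.5 x 0.84 / (1 - 0.25 x 0.16) = 0.126 / 0.96 = 0.13.
- r = 0.3, a_M = 0.5, a_L = -0.3: the L slope is -0.0756 / 0.9856 = -0.077, so the difference is 0.131 + 0.077 = 0.21.
- r = 0.4, a_M = 0.5, a_L = -0.3: 0.175 + 0.102 = 0.28.
- r = 0.2, a_M = 0.3, a_L = 0: 0.0504 / 0.9856 = 0.05.
- Equal links: the two slopes cancel and the interaction is 0.

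**Rough rejection rate.** With unit variances, the standard error of the interaction is about sqrt(1/51 + 1/51) = 0.198. In the first case 0.131 / 0.198 = 0.66, and the chance of crossing ±1.96 is Φ(-1.30) + Φ(-2.62) = 0.097 + 0.004, about 10%.

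**Simulation.** The fitted model was FC on arm, zone adherence, arm x adherence, age and sex, with and without baseline CRF (4,000 replicates, 51 per arm). False-positive rates for arm x adherence:

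| r | a_M | a_L | Without CRF | With CRF | Mean spurious interaction without CRF |
|---|---|---|---|---|---|
| 0.3 | 0.5 | 0 | 10.4% | 5.1% | 0.13 |
| 0.3 | 0.5 | -0.3 | 16.8% | 5.2% | 0.21 |
| 0.4 | 0.5 | -0.3 | 28.0% | 4.8% | 0.28 |
| 0.2 | 0.3 | 0 | 5.1% | 4.4% | 0.05 |
| 0.3 | 0.4 | 0.4 | 4.4% | 4.6% | 0 |

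The mean interactions match the formula, and repeat runs gave rates within about two points. With r = 0.3 and a link of 0.3 in M only, the rate was 6.1%.

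**Three variations**, run separately with 3,000 replicates and with r defined as a partial correlation:

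- *Equal links.* With r and both links at 0.4 (N = 120), the interaction is not inflated (4.3%), but the adherence slope within M is falsely significant in 19.1% of trials.
- *Change in FC as the outcome.* The interaction rate is 4.3% to 5.7% when fitness does not predict change. It was 7.8% when fitness did (r = 0.3, a_M = 0.4, added slope 0.3).
- *CRF measured with error.* With assumed reliability 0.8, adjustment leaves 5.9% to 7.1%.

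**The case against.** The strongest reply has four parts.

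*The fitness-to-zone link is inferred.* A reader might take the protocol to say that low fitness makes people miss the zone. It does not: it speaks of physical or motivational constraints and never names fitness. Section 15 also sets each target heart rate from that person's baseline maximal test, uses perceived exertion where the two disagree, and builds intensity up gradually. All of this weakens the link. The opposite-sign scenarios need fitter L participants to be out of zone more often, whereas the protocol attributes L overshoot to expectations. This stands, and it is why the lower figures deserve as much weight as the higher ones.

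*Attendance.* A reader might extend the argument to the sessions-completed models. No text links fitness to attendance, and the different zone definitions have no counterpart there. The objection stands.

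*The outcome may be change.* Section 17 speaks of training-induced change, and the Aim 3 statement about CRF is cross-sectional. If the outcome is change in FC and fitness does not predict change, the inflation disappears. But the model being extended uses end-of-study FC with no baseline FC term, so as written the plan cannot rely on this protection.

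*The analyses are exploratory.* ITT remains the main analysis for all three aims, and the plan calls it the best basis for inference. A reader might infer that the adherence models exist to explain a null ITT result. The documents give no such purpose: their rationale is dose-response and variation in achieved intensity. The closing sentence of the section also already speaks of gains associated with adherence. This lowers the stakes but does not remove the bias from the models.

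**Conclusion.** The concern holds for the HR-zone interaction models, at modest size and conditionally. They test a post-randomisation moderator without adjusting for a measured baseline variable that the protocol itself ties to FC and learning. If fitness relates differently to zone adherence in the two arms, the interaction is biased. In the scenarios tried, the false-positive rate at a nominal 5% was about 10% for a link of 0.5 in M only, 17% to 28% for opposite-sign links, and 5% to 6% for weak links in M only. There was no inflation with equal links, or with a change outcome that fitness does not predict. Every correlation behind these figures is an assumption.

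The documents do not support the stronger readings that the trial's main conclusions are at risk, or that the attendance models are shown to be biased. The ITT analyses do not use these terms.

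**What to change.** In Section 17 of the Protocol and of the SAP, add baseline CRF (VO2 from the baseline maximal test) as a covariate in every model that interacts group with the share of sessions in the prescribed HR zone. The same covariate may go into the attendance models for consistency, though the documents give no specific reason for it there.

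In the sentence that introduces these analyses, in both documents, replace *affects* with *is associated with*. Adjustment does not reach motivation, which the protocol names as a cause of missed zones, and measurement error in CRF leaves some residual bias.

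The cost is one degree of freedom in exploratory models and a change of wording. The test is already part of screening, so no new data are needed. Where a test misses the criteria for a true maximum, Section 11 of the Protocol already says the VO2peak result will be considered as a possible covariate; the revised text should say how such values enter these models.

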Following the acute exercise session, participants will continue to the second phase by entering one of two training groups, as determined by their initial randomization:

- **Moderate intensity exercise training** will be a 24-week supervised cycling program, with supervision directly from our research team. Participants will start in waves of ~5 per wave. All participants will first receive a one-on-one orientation with an exercise training specialist that has been trained by [name] in monitoring an exercise program for healthy older adults. Since participants will initially be relatively inactive, the exercise group will start with a 5 minute-warm-up, 20-minutes moderate intensity cycling at 50-60% Heart Rate Reserve (HHR) and 20 minutes passive cycling, and 5 minute cool-down per session, for 3 sessions/week. In each additional week, we will replace 5 minutes of passive cycling with 5 minutes of moderate intensity cycling per session, until the total time for moderate intensity is 40 minutes per session by the start of week 5 (with additional 5 minute warm-up and 5 minute cool-down). Starting at week 6 the exercise group will increase their moderate intensity cycling to 60-70% HHR with a similar build up to the first 5 weeks. Starting at week 13 the exercise group will increase their moderate intensity cycling to 70-80% HHR with a similar build up to the first 5 weeks. This program allows for a gradual build-up of endurance while including training for approximately 135 minutes of moderate-to-vigorous intensity exercise per week.
- **Functional fitness training** will be a 24-week supervised exercise program designed to focus on functional flexibility and mobility, with supervision directly from our research team. All participants will first receive a one-on-one orientation with an exercise training specialist that has been trained by [name] in monitoring an exercise program for healthy older adults. Training will start with a 15 minute-warm-up of stretching, 20 minutes of light intensity cycling and 15 minutes of dynamic stretching to increase range of motion and functional fitness, for 3 sessions/week. In each additional week, additional stretches will be added to maintain variety and improve flexibility of all major muscle groups. Our goal is to maintain HR at or below 40% HRR during training sessions for this group.

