Both groups will wear a Heart Rate Monitor (Polar wrist watch and chest-band) during their exercise sessions. We will download HR monitor data following each session and this data will be used to give feedback on their target HR for the following session. Target HR for each condition will be based on the baseline maximal exercise test. Ratings of perceived exertion (RPE) will also be collected during the baseline max test, and in cases where there was a discrepancy between expected RPE and HR during this test, RPE will be used in conjunction with HR in developing a target HR for moderate and passive cycling sessions.

All training sessions in the first two weeks are scheduled to be in our lab. After the first two weeks, participants can do up to two sessions per week outside the lab. At the conclusion of each training session in the lab, participants are given instructions on how to complete their training at home including use of the HR monitor. In order to maintain blinding to intensity prescriptions, participants are guided to mimic the heart rate zones they are targeting in their lab sessions. For participants that live outside of a 30-mile radius, we have an additional option for more frequent home training sessions, provided that participants demonstrate they can charge and upload their HR data to Polar Flow (online) for trainer review and feedback at least once per week.

16. General Data Management/Quality Assurance

Paper/hard copy records (hard copy surveys, questionnaires, case report forms, pictures, etc.)

- Standardized procedures will be used to collect and maintain basic demographic and health data on all participants, including: (1) collecting names, email addresses, and phone numbers; (2) contacting participants with personalized letters and cards via email; (3) maintaining phone contact with participants throughout the study; (4) setting up a (secure and access-restricted) tracking file with names, email addresses, phone numbers, projected session times.
- All contact information will be stored on a secure file server and will be kept separate from study data. Once a participant has been contacted and screened with our screening session, and qualifies for the study, they will be assigned a subject number and all testing materials beyond that point will contain only the subject number.

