Once a participant passes screening during their maximal exercise test as described above, exercise training sessions are each supervised in our lab at Spence Labs by a trained exercise specialist. Personnel involved in exercise training will be required to be certified in CPR and First Aid. Lead exercise trainers will be Clinical Exercise Physiology Master's students recruited from the Health and Human Physiology Department at the University of Iowa. In addition, we require that trainers have had previous experience in training older adults.

To protect against potential adverse events during exercise training, the exercise training lab is equipped with an AED, a phone to call 911, and during all exercise sessions we monitor heart rate, blood pressure, and perceived exertion to ensure we are aware of any discomfort that would be a warning sign for an adverse event. All training sessions include a cool-down that is designed to ensure participants' heart rate and blood pressure are back to near resting levels before leaving our training site. In the event that a participant expresses symptoms of a potential adverse event to exercise (e.g., light headed or an unusually high spike in heart rate or blood pressure), exercise trainers will immediately stop exercise and have the participants rest with the opportunity to drink water. If there is any sign that the symptoms are not resolving from a break in exercise, the trainer will call 911 to ensure timely arrival of an emergency medical team to our training site. Because our training site is a 10-minute drive and 20-minute walk from the hospital, and our team doctors could also be working at clinics up to a 25-minute drive away, the safest response to any potential medical event will be to call 911.

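### Section 18 describes every training session as supervised in the lab and monitored, but Section 15 permits up to 44 of 72 sessions elsewhere (at most 66 for distant participants), and the stop, 911 and event-reporting steps are not written for those sessions.

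*Protocol*

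**What the plan says.** **Supervision.** Section 18 of the protocol says that, once a participant has passed the maximal exercise test, "exercise training sessions are each supervised in our lab at Spence Labs by a trained exercise specialist". It adds that heart rate, blood pressure and perceived exertion are monitored at all exercise sessions and that the training lab has an AED. If symptoms appear, the trainer stops the exercise and, if they do not settle, calls 911 to the training site. Section 15 describes the moderate-intensity arm in the same spirit (it "will be a 24-week supervised cycling program, with supervision directly from our research team") and says much the same of the functional fitness arm.

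**Sessions outside the lab.** Section 15 also schedules only the first two weeks entirely in the lab: "After the first two weeks, participants can do up to two sessions per week outside the lab". For those living beyond a 30-mile radius, "we have an additional option for more frequent home training sessions", provided that they can upload heart-rate data "for trainer review and feedback at least once per week". At the end of lab sessions "participants are given instructions on how to complete their training at home including use of the HR monitor". On monitoring, Section 15 says "We will download HR monitor data following each session". Section 16 lists "maintaining phone contact with participants throughout the study", without a schedule.

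**Finding and reporting events.** Section 19 expects adverse events to be identified most likely when the participant reports one to staff during a session or testing appointment. Section 18 requires a written account within 24-48 hours of the event, or 24 hours if it is potentially serious. Section 19 requires serious events to be forwarded within 24-48 hours of occurrence. The SAP covers efficacy and adherence analyses only and adds nothing on safety.

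**The concern.** The safety section credits every session with safeguards that depend on a trainer being in the room, while the intervention section permits sessions where none is described as present. An ethics or monitoring board member who reads Section 18 alone would judge the risk on the wrong footing.

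Two practical matters follow. First, the stop and 911 steps are written for a trainer at the training site, so they do not tell a participant exercising elsewhere what to do. Second, an event at an outside session has to be volunteered by the participant at a later contact, while the deadlines above count from the event.

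Home sessions are not incidental. Section 17 and the SAP both plan a comparison of lab and home heart rates, and predict higher heart rates at home in both groups. The participants are previously inactive adults aged 55 to 80, and the moderate arm's target rises to 70-80% of heart rate reserve from week 13.

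Section 19 also intends to contrast side effects between the arms. Reports volunteered when contact happens are a weaker basis for that than the same question put to everyone.

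**Working it through.** The documents give no total for lab or home sessions, so there is no stated figure to reproduce. The counts follow from the schedule in Section 15.

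**Inputs.** Both arms run 24 weeks at 3 sessions a week. Weeks 1-2 are in the lab. From week 3, up to 2 sessions a week may be outside. Beyond 30 miles the allowance is more frequent, with no cap stated.

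**Session counts.**

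- Total: 24 × 3 = 72.
- Weeks with an outside allowance: 24 − 2 = 22.
- Standard rule, maximum use: 22 × 2 = 44 outside, 44/72 = 61%. In the lab: 72 − 44 = 28, or 39%.
- Standard rule, one outside session a week: 22 × 1 = 22, 22/72 = 31%.
- Distance option, upper bound: 22 × 3 = 66 outside, 66/72 = 92%. In the lab: 6, or 8%. This assumes that the two-week lab start also applies to distant participants and that the option can cover all three weekly sessions. In any week where it is used beyond the standard two, no lab session remains.
- Moderate arm, weeks 13-24: 12 × 3 = 36 sessions, of which up to 12 × 2 = 24 may be outside under the standard rule and at most 36 under the distance option. Section 15 describes a build-up into this block, so not every one of these sessions is fully at the top intensity.

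**Safeguards side by side.**

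| Safeguard | Lab session (Section 18) | Outside session (available text) |
|---|---|---|
| Live trainer | Yes | Not described |
| Heart rate | Monitored live | Recorded, reviewed afterwards |
| Blood pressure | Monitored | Not described |
| AED | In the lab | Not described |
| Stop for symptoms | Trainer stops exercise | Not described; content of home instructions not shown |
| 911 | Trainer calls, to the training site | Not described; content of home instructions not shown |

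**Reporting clock.** Under the standard rule at maximum use, one lab session a week remains. If it falls on the same weekday each week (an assumption), an event just after it could wait up to 7 days, or 7 × 24 = 168 hours, before the next lab contact. The longest event-based deadline is 48 hours. Weekly data review for distant participants gives a similar interval, and a heart-rate trace does not show symptoms such as light-headedness or chest pain. A call from the participant or an intervening phone contact would shorten the wait, but the available text requires neither within a stated time.

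**The case against.** The strongest reply is that the Section 18 paragraphs are about the lab: they name it, list its equipment and refer to leaving the training site. Section 15 permits home sessions openly and Section 17 analyses them, so nothing is hidden. That makes a lab-only reading possible, but *each* and *all* carry no such limit, and a safety section should not need another section to correct it.

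A reader might go further and infer that the trial gives home participants no emergency instructions. The documents do not support that. The consent pages were removed before review and the home-training instructions are not reproduced; either could contain them. Likewise, an AED or blood pressure cuff at outside sessions is not described, which is not the same as known to be absent.

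The counts are permissions, not estimates: 61% requires full use of the allowance every week, and 92% requires the distance option to cover every session after week 2.

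On reporting, Section 19 calls contact-time reports the most likely route, not the only one. Phone contact exists, and late awareness can occur in any trial with gaps between contacts. The Appendix III form already has a yes/no adverse-event question, but Section 19 has the report form completed after an event is identified, and no schedule for asking the question is given. The home rule and the reporting route are the same in both arms, so differential ascertainment is not shown.

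Other protections also stand: a physician-monitored maximal test with exclusion for cardiac findings, exclusion of high-risk participants, the two-week lab start, and the illness and injury rules in Section 20. They lower the risk, but they do not say what to do when symptoms begin during a session at home.

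**Conclusion.** The concern holds in a limited form. As written, Section 18 is inaccurate for sessions that Section 15 allows: up to 44 of 72 under the standard rule and at most 66 of 72 under the distance option. For those sessions the protocol describes neither live supervision nor a blood pressure check, and its stop and 911 steps do not reach them. Whether participant-facing material fills that gap cannot be determined from the available text.

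Because detection rests mainly on participant reports at contact while deadlines run from the event, an event at home may surface after the deadline. How often is unknown, since neither home use nor event rates are given. It would be too strong to conclude that most sessions are in fact unsupervised, or that deadlines will be missed; the documents show only that both are possible.

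This should be corrected as a safety and reporting matter. It has no bearing on the primary analysis or the sample size.

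**What to change.** 1. In Section 18, limit the *each* and *all* statements to lab sessions, and say what monitoring applies outside the lab.
2. For outside sessions, state a rule set by the study physicians: which symptoms mean stop, when to call 911, and that staff are told the same day. If the home instructions or consent form already contain this, a cross-reference is enough. Word it by symptoms and keep it identical in both arms, so that it does not reveal the intensity prescription.
3. In Section 19, add one scripted question, asking about any adverse events since the last contact, put in the same words to both arms at each lab visit or data review, and at least weekly for distant participants. The yes/no item on the Appendix III form can be adapted.

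The cost is a short amendment, a few lines in the existing home instructions and one question at contacts that already take place. Asking will probably bring in more minor events to record. No new staff or visits are needed.
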